Our primary aims are to evaluate the feasibility of a larger study and examine preliminary data regarding benefit and tolerability of an essential oil formulation distributed by Young Living Essential Oils, Lehi, UT., for enhancing QOL in children with ASDs. We will develop preliminary data suitable to be submitted in a competitive NIH grant application for a larger multisite study. The proposed study will include a 7-month crossover with two 3-month conditions and a month washout between, with randomly assigned order. The 2 conditions will be a proprietary formula of essential oils and a scented coconut oil comparator. Measures of QOL, equanimity, and sleep health will include parent report on valid and reliable rating scales.

Primary Hypotheses

1. We can recruit 28 participants in 2 years with 85% adherence and 85% retention through both conditions.

- 2. With essential oils, participants will show significantly improved QOL on the Pediatric Quality of Life Inventory compared to the control condition, with a medium effect size.
- 3. While receiving essential oils participants will show negligible or no increases in adverse events (AEs), including allergic contact dermatitis, immediate contact reactions (contact urticaria), and photosensitivity, compared to the control condition.

Secondary Mediational Hypotheses

- 1. With essential oils, compared to the control condition, participants will show significantly improved sleep onset and maintenance on objective and subjective measures (actigraphy; parent sleep diaries, and parent and clinician-rated scales) with a medium effect size, and this will mediate the improvement in QOL.
- 2. With essential oils, compared to the control condition, participants will display greater equanimity and improvements in mood and daytime behavior on objective and subjective measures (heart rate; parent and clinician rated scale) compared to the control condition and this will mediate the improvement in QOL.

Participant Inclusion/Exclusion Criteria

Inclusion Criteria

Entry criteria are the following:

- i. Outpatients between 3 and 9 years of age, inclusive;
- ii. Diagnosis of Autism Spectrum Disorder (ASD) by DSM-V;
- iii. Total item mean score of > 1.5 on PedsQL Inventory;
- vi. Care provider who can reliably bring subject to clinic visits and provide trustworthy ratings.

Exclusion Criteria

Exclusion criteria are the following:

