- i. Bipolar disorder by Child & Adolescent Symptom Inventory (CASI, Gadow & Sprafkin, 1997) and clinical interview/history, or major depression accompanied by family history of bipolar disorder;
- ii. Children with allergies to essential oils;
- iii. Children with seizure disorder/epilepsy;
- iv. Significant physical illness (e.g., serious cardiovascular, liver, or renal pathology);
- v. Medications specifically given for insomnia and exogenous melatonin, which have the potential to confound study results, within the previous 2 weeks before baseline;
- vi. Anticipated changes of doses of medication or other medical treatments or supplements;
- vii. Weight less than 10 kg;
- viii. Sleep Disordered Breathing (SDB) as defined by a total score of ≥ 3 on the CSHQ SDB subscale and parent report;
- ix. Nut allergies;
- x. Allergy to vanilla;
- xi. A substantial trial of essential oil use within the past 6 months (i.e., consistent use for 6 weeks).

METHODS

Study Design

This study will use a double-blind -controlled crossover design with random assignment to order of conditions. The 2 conditions will be ReconnectTM, a mixture of essential oils formulated by Young Living (YL) vs. a fragrant appearance-matched coconut-oil comparator. In order to randomize 28 children we anticipate that approximately 36 children will be screened. There will 2 conditions in the crossover design.

Participants will receive Reconnect or scented coconut oil comparator for 3 months following the Baseline visit. At the end of 3 months, participants will be administered all endpoint measures for that condition. Then there will be a 1-month washout prior to the start of the second condition. At the end of the second 3-month condition, participants will again be administered all endpoint measures for that condition. The endpoint assessment for the 2nd condition will be 7 months from original baseline. During the 1st condition participants will be evaluated at 2 week intervals for the first month to assess whether the mode of essential oils application is tolerable (i.e., inhalation or topical application) and to develop graphs of effect on sleep and equanimity over time. During the final 8 weeks of condition one, participants will be seen monthly. During the second condition we will have established that the modes of application are tolerable and subjects will be evaluated at 3 monthly visits. There will be 10 visits to the Center including the Screening and Baseline Visits.

Procedures

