To be applied only by a trusted adult or under adult supervision.

Topical: Apply 1 drop to the back of the neck and 1 drop to the feet. Rub in the oil for 30 seconds to 1 minute. Each bottle has an orifice that allows the oil to be expelled drop by drop. Dilution is not required, except for the most sensitive skin. Apply in the morning.

Aromatic Method: Diffuse one diffuser-full (8-12 drops of oil in water) at night.

- 1. Home diffuser instructions: Open the water reservoir by lifting the lid. Add room-temperature water (distilled water is recommended) up to the fill line of the reservoir. Do not exceed the fill line.
- 2. Add 8-12 drops of Reconnect to the water.
- 3. Replace the lid to cover the water reservoir.
- 4. Plug in the Home Diffuser and push the power switch to start diffusing.
- 5. When water runs out, the diffuser will automatically shut off.
- 6. To cycle through the three-mode power settings, press the power switch quickly: Mode 1: Green light Constant diffusion Mode 2: Red light 30 seconds intermittent diffusion Mode 3: Off. Use constant diffusion (green light, mode 1).
- 7. To turn on/off the ambient LED light, press and hold the power switch for approximately 2 seconds.

Notice: Due to the mist output of the Home Diffuser, use caution on surfaces that are sensitive to water.

Essential Oil

The type of Young Living essential oil we will be utilizing is ReconnectTM. ReconnectTM contains the following ingredients: Caprylic/capric triglycerides, Prunus amygdalus dulcis (Sweet almond) oil, Boswellia sacra† oil, Citrus aurantium bergamia† peel oil, Commiphora myrrha oil, Lavandula angustifolia† oil, Pelargonium graveolens† flower oil, Callitris intratropica wood oil, Santalum paniculatum† wood oil, Cananga odorata† flower oil, Cedrus atlantica† wood oil, Aniba rosaeodora† wood oil, Melissa officinalis† leaf oil, Picea pungeons†

branch/leaf/wood oil, Picea mariana leaf oil, Hyssopus officinalis† leaf oil, Rosa damascena† flower oil. The comparison oil is coconut oil with a tiny amount of vanilla, just enough for an aroma. Please see Table 2 for a listing of the ingredients, their current common uses, and potential side effects.

Primary Outcome Measure

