Caprylic/capric triglycerides	Ester derived from Coconut oil; Good solvent and emollient, acts as a	Skin exposure shows very low toxicity and no potential for skin/eye irritation/sensitization; FDA approved as a food additive and CIR approved for cosmetic use	Derived from coconut oil and glycerin	"Caprylic/Capric Triglycerides." Truth in Aging . Truthinaging.com, 2013. Web.

	carrier for fat-soluble vitamins; used in cosmetics: hair products, dyes, sunscreen, deodorants, make-up			
Cedrus atlantica (Cedarwood) wood oil	Acne, arthritis, coughing, dermatitis, bronchitis, stress	No special precautions indicated	Atlantone, caryophyllene, cedrol, cadinene	"Atlas Cedarwood Essential Oil." AromaWeb . AromaWeb, LLC, 2014. Web.
Melissa officinalis leaf oil	Antidepressant, sedative, antispasmodic, hypotensive; helps with nausea, headaches	Non-toxic, but could be irritating or sensitizing so should be diluted and not used on sensitive skin	Tannins, eugenol, terpenes, citronellal, octyl benzoate, linalool, nerol, etc	"Melissa Essential Oil (a.k.a. Lemon Balm Essential Oil) Information." Esoteric Oils . Esoteric Oils CC, 2014. Web.
Picea pungens (Idaho blue spruce) branch/leaf/wood oil	Relax the mind and muscles, relieve muscle tension, cleanse minor skin irritations	FDA approved as a Food Additive, so generally safe	45-55% monoterpenes (mostly α-pinene and limonene); 3-12% sesquiterpenes	"Idaho Blue Spruce Essential Oil." Aromatherapy Living with Young Living Essential Oils. Young Living Essential Oils, 2012. Web.

Table 3. Ingredients of coconut oil scented with 0.5% vanilla absolute oil, their uses/actions, and potential side effects.

Scented Coconut Oil	Uses	Safety	Chemical Composition	Citations
Ingredient				
Vanilla Absolute Oil	Found in Madagascar. Used primarily as a fragrance.	A solution of 10% vanillin diluted in petrolatum resulted in occasional contact allergy. In a study by Hausen, no positive reactions to vanillin were found.	Primary constituents include vanillin, vanillic acid, and phydroxybenzaldehyde	"Certificate of Analysis: Vanilla Absolute." Eden Botanicals . Eden Botanicals, 2015. Web. Wöhrl, S., Hemmer, W., Focke, M., Götz, M. and Jarisch, R. (2001), The significance of fragrance mix, balsam of Peru,

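### The allergy exclusions name the comparator's 0.5% vanilla scent but not coconut, its main ingredient, so a child with known coconut allergy could be judged eligible

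*Combined protocol and SAP*

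**What the plan says.** Three of the eleven exclusion criteria concern allergy: ii "Children with allergies to essential oils", ix "Nut allergies" and x "Allergy to vanilla". None mentions coconut, and the nut criterion is not defined.

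The Essential Oil section describes the control product: "The comparison oil is coconut oil with a tiny amount of vanilla, just enough for an aroma". The later ingredient table for the comparator (labelled Table 3) gives the strength in its title: "Ingredients of coconut oil scented with 0.5% vanilla absolute oil". It has two rows, vanilla absolute and coconut oil.

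Reconnect's ingredient list begins with caprylic/capric triglycerides, whose composition Table 2 gives as "Derived from coconut oil and glycerin".

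Under Background and Significance, both groups cross over after a washout, so each child is due to receive both oils. Under Procedures and Dosing, the oil is massaged onto the feet and neck in the morning and diffused in the evening.

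Primary Hypothesis 3 expects negligible or no increase in adverse events on Reconnect, "including allergic contact dermatitis, immediate contact reactions (contact urticaria), and photosensitivity, compared to the control condition".

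**The concern.** The allergy criteria appear to have been built from the ingredients: one for the essential oils, one for the almond oil and one for the comparator's scent. The base of the comparator was left out. Anyone comparing the list with the composition of the two oils will see that the minor component of the control product is screened for by name and the major one is not.

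Two things are at stake. The first is safety at entry: children aged 3 to 9 could have a product applied to the skin and diffused for 12 weeks when its main ingredient is one to which they are known to be allergic. The second is the safety comparison. Contact dermatitis and contact urticaria are named in a primary hypothesis with the comparator as reference, so a preventable reaction to the reference product would make Reconnect look relatively safer.

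**Working it through.** The plan states no figure to reproduce. The check sets the ingredients beside the criteria.

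| Ingredient | Where listed | What its safety entry says | Exclusion that names it |
|---|---|---|---|
| Essential oils in Reconnect | Essential Oil; Table 2 | Varies; several mention irritation or sensitisation | ii |
| Sweet almond oil (Reconnect) | Table 2 | Carries a nut/almond allergy flag | ix |
| Caprylic/capric triglycerides (Reconnect) | Table 2 | Coconut-derived; rated as having no sensitising potential on skin | none |
| Vanilla absolute, 0.5% (comparator) | Table 3, ingredients | Occasional contact allergy to 10% vanillin; another study found no positive reactions | x |
| Coconut oil (comparator) | Table 3, ingredients | No allergy warning | none |

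**Step 1: is coconut covered by another criterion?** Criterion ii does not name it. Criterion ix might cover it if the screener counts coconut as a nut. The documents neither say so nor rule it out, and the one nut warning in the tables is attached to almond. Eligibility is therefore left to the screener's reading.

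**Step 2: which exposure is supported?** For the comparator, exposure to coconut oil itself is certain for every child who reaches that condition. If the product holds only the two listed components, coconut oil makes up 100% − 0.5% = 99.5% of it. That describes composition; it does not measure allergenic risk. For Reconnect, the documents show a coconut-derived ester in an unstated amount, with an entry denying sensitising potential.

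**Step 3: what could it do to Hypothesis 3?** If all 28 children complete the comparator condition, one child who reacts to coconut oil there adds 1/28 = 3.6 percentage points to the control reaction proportion. With prevalence p of unscreened coconut allergy among enrolled children, the expected number is 28 × p. This reaches one child only when p = 1/28 = 3.6%, and is below one for any smaller p. The documents give no p and no probability that an allergic child would react, so the expected effect can be bounded only in this conditional way.

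**The case against.** The best defence is that the list follows the plan's own safety tables. Almond carries a nut warning and vanillin a contact-allergy note, and both are excluded. The coconut entry carries no warning, describes the oil as commonly used on skin, and reports no adverse effects in populations that eat a great deal of it. This explains how the omission arose, and it is true that the documents identify no general coconut hazard. But that entry cites dietary use and an opinion on packaging material. It does not address a child already known to be allergic, which is the question an entry criterion answers. Vanilla is excluded on thin evidence at a low concentration, so the plan's own threshold for a named exclusion is low.

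A second defence is that a sensible screener would read the nut criterion as including coconut, or would learn of the allergy from the medical history at Screen. That may well happen. It means that such a child could be enrolled, not that one would be. It does not make the rule explicit or uniform.

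A third is monitoring: adverse events and skin are checked at every visit after Baseline, and a physician may stop the oils or switch the mode. These checks follow exposure. They are also later for children who take Reconnect first. In Table 1 those children start the comparator at Week 16 and are next seen at Week 20, whereas children who start on the comparator at Week 0 are seen at Week 2.

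A reader might go further and infer that a coconut-allergic child is exposed to the allergen in both conditions. The documents do not support this: they do not show that the ester in Reconnect carries coconut allergen, and Table 2 points the other way. The inference would also weaken the argument about Hypothesis 3, since a child who reacted to both oils would add to both counts and the difference would tend to cancel.

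**Conclusion.** The gap is real but narrow. Read literally, the criteria allow a child with known coconut allergy and no nut allergy to be randomised and to receive coconut oil by both routes in the comparator condition. The conclusion rests on the undefined nut criterion not being read to include coconut, and on the allergy not being acted on at screening for some other reason.

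Any resulting contact reaction would fall on the control side of Hypothesis 3 and so flatter Reconnect. One might infer from the 3.6 points per child that the safety comparison is materially biased. That is not shown. The figure is conditional on an allergic child enrolling and reacting, prevalence is not given, and the expected effect is probably small. The Data Analytic Plan also tabulates adverse events by type, severity and attribution for each condition, so a single such event would be visible.

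The point merits a change because it decides who may be enrolled, concerns young children, and costs almost nothing to settle.

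**What to change.** Reconcile the exclusion list with the ingredient tables. Criteria ix and x could become one: known allergy to nuts, coconut, vanilla, or another listed ingredient of either study oil. If the sponsor prefers a smaller edit, the minimum is a statement of whether criterion ix includes coconut. In either case, add a direct question on coconut to the medical history that Table 1 already schedules at Screen, so that all screeners apply the same rule.

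The cost is one line of protocol text and one screening question. The downside is that an occasional child is excluded. No change to the sample size or the analysis is needed.

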All participants must have significant problems with QOL as measured by the PedsQL Inventory, with a total item mean score of ≥ 1.5 (i.e., one standard deviation below the normative mean).

At baseline, participants will be randomly assigned to one of two orders of essential oils. The oil will be dispensed at the Baseline visit, and will be administered by both massaging the oil on the feet and the back of the neck in the morning and by the diffusion method in the evening.

In this study, clinical responders will be defined as showing a 30% improvement in the total score of the PedsQL Inventory.

Approximately 50% of children will wear a device known as an actigraph that measures activity level and sleep quality. There will be 6 actigraphs and they will be assigned to participants as they are made available on a first come first serve basis. There may be some participants who are unwilling to wear the actigraph and for those who are tactiley defensive we will not require them to do so. Participants will wear the devices for five consecutive nights, on three separate occasions (i.e., between Screening and Baseline, prior to the End Point of the first 3 month period, and prior to the End Point of the second 3 month period). The small watch-like devices worn on the wrist or ankle will collect activity data and measure body temperature while the participant sleeps. They will yield the following sleep variables: 1) time in bed, 2) total sleep time (from lights out), 3) sleep onset latency, 4) morning waking time, 5) frequency of night

wakings, 6) longest sleep period, and 7) sleep efficiency. This is a reliable method of objective data collection for sleep-wake patterns including timing, continuity, and duration of sleep.

In the proposed study, there will be a primary clinician (the physician) and an independent evaluator. The physician will discuss possible side effects and make dose or administration mode adjustments. The independent evaluator will interview the parents with respect to target improvements (QOL) and make DD-CGAS ratings based on all feedback, including parent rating scales.

Dosing

Each participant will utilize both oil delivery methods: diffusion at night and topical application in the morning. If a participant is unable to tolerate one of these delivery methods, then both the morning and night-time doses can be administered via the same, more tolerable method.

ReconnectTM Directions:

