Laboratory Tests. On three separate occasions during the study participants will have blood drawn and laboratory tests will be conducted to assess any changes in test values since the Screening Visit. Blood and urine will be collected at the Screen Visit, at the Endpoint of the first phase (Week 12), and at the Endpoint of the last phase (Week 28). The following tests will be run on the blood samples: ALT, AST, total and direct bilirubin, creatinine, CRP, IL-6, and CBC. The following tests will be run on the urine samples: standard urinalysis, to evaluate protein, PH, glucose, ketones, nitrites, appearance, color, specific gravity, and bacteria.

Adverse Events (AEs). To minimize the risk, subjects will be systematically monitored. AEs, vital signs, including resting BP, will be evaluated at each visit throughout all phases of the study. When the treating clinician elicits an AE, it will be documented on a case report form, regardless of suspected relationship to the essential oil. For all AEs, the investigator will obtain sufficient information to determine the onset, course, and outcome of the AE. If a subject has experienced an AE, the subject may return to the site for an unscheduled visit at the PI's discretion. If any of these AEs are serious and/or unexpected, the site PI will contact the Sponsor and notify the IRB as appropriate.

Potential AEs include sun sensitivity due to the Bergamot in the essential oil, possibly gynecomastia in pre-pubescent males due to the lavender oil in the essential oil, and skin irritation at the application site.

Sample Characteristics

Demographic Profile. This will be completed by the parent / caregiver at screening to document basic demographic information (parent education, occupation, and marital status).

Cognitive / Developmental Measures. Depending on the age and functioning level of the child, the Stanford-Binet Intelligence Scales; 5th Edition abbreviated battery (Nagle & Bell, 1993) or Mullen Scales of Early Learning AGS Edition will be administered (Mullen, 1995). These are the two cognitive/developmental measures used in the Autism Treatment Network and our other projects. We will evaluate level of cognitive functioning to characterize our sample. The IQ test results will be used to characterize our sample via mean and standard deviation.

Social Validity

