Prunus amygdalus dulcis (Sweet Almond) oil	Protects skin's barrier function and keeps it from drying - used in body lotions, face creams, and body oils; anti- inflammatory and pain relieving	CIR approved as safe for topical application; absorbs slowly through skin; completely digested if taken orally; non-irritating and non-sensitizing in any concentration **Nut/almond allergies	Oleic acid (62-86%), Linoleic acid (20- 30%), other fatty acids, α-tocopheral, arginine, phytosterols, polyphenols	Almond oil (prunus amygdalus dulcis) – the universal skin oil (n.d.). Bio G Cosmetics. Web.
Boswellia sacra oil	"Frankincense." Perfumes and skin care; edible. Potential anti-depressant. Studies suggest it may have cancer- killing properties and improve osteoarthritis.	Not CIR or FDA approved, but widely used and appears to be well tolerated	Acid resin (56%), gum (similar to gum arabica) (30-36%), 3- acetyl-β-boswellic acid, α-boswellic acid, incensole acetate, phellandrene	Martin, N. (n.d.). Sacred Frankincense Essential Oil - The Original Oil Given to Baby Jesus? Experience-Essential-Oils.com. Web.
Citrus aurantium bergamia peel oil	Helps with heartburn, gas, insomnia, mild depression, and upset stomach (Martin).	FDA approved as a Food Additive and generally regarded as safe, but not recommended for children < 5 years old and can result in skin irritation, particularly from frequent usage or UV light exposure (Martin).	α-pinene, myrcene, limonene, α- bergaptene, β- bisabolene, linalool, linalyl acetate, nerol, neryl acetate, geraniol, geraniol acetate and α- terpineol (Bergamot)	Bergamot essential oil information (2014). Esoteric Oils CC. Web. Martin, N. (n.d.). The Benefits of Bergamot include Easing Stress from Mind & Body! Experience-Essential-Oils.com. Web.
Commiphora myrrha oil	Helps clear colds, bronchitis, cough by removing mucus; used for chapped skin, eczema, skin ulcers, ringworm, skin wounds	Non-toxic, non-irritating, and non-sensitizing	α-pinene, cadinene, limonene, cuminaldehyde, eugenol, m-cresol, heerabolene, acetic acid, formic acid	Myrrh essential oil information (2014). Esoteric Oils CC . Web.

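### The printed topical directions put a bergamot-containing oil on the back of the neck in the morning, normally without further dilution and with no sun precaution, although the protocol lists sun sensitivity as a potential AE

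*Combined protocol and SAP*

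**What the plan says.** The topical part of the Reconnect Directions (Dosing section) reads "Apply 1 drop to the back of the neck and 1 drop to the feet" and then, after the instruction to rub the oil in, "Dilution is not required, except for the most sensitive skin. Apply in the morning". The Procedures section gives the same sites and time of day for the study oil: "massaging the oil on the feet and the back of the neck in the morning". This is therefore the trial regimen and not only product-label text. If one delivery route is not tolerated, "both the morning and night-time doses can be administered via the same, more tolerable method".

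The Essential Oil section includes bergamot peel oil in the blend. The list opens with carrier oils: "Caprylic/capric triglycerides, Prunus amygdalus dulcis (Sweet almond) oil".

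Three places recognise a light-related skin risk:

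- Safety Measures, Adverse Events: "Potential AEs include sun sensitivity due to the Bergamot in the essential oil".
- Table 2, Safety column for bergamot: "can result in skin irritation, particularly from frequent usage or UV light exposure".
- Primary Hypothesis 3, which names photosensitivity among the events to be compared with control.

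The directions do carry other precautions: adult application or supervision, dilution for the most sensitive skin, and, for the diffuser mist, "use caution on surfaces that are sensitive to water". None concerns sun.

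**The concern.** A family following the directions as printed would put an oil with a protocol-named sun-sensitivity risk on a child's neck ahead of the daylight hours. The neck may well be uncovered, although that is an assumption. The directions would give the family no means of avoiding the reaction. The participants are children aged 3 to 9, and in a crossover every child who completes both conditions receives this exposure. At stake is an avoidable skin reaction. Power, type I error and the estimate of the quality-of-life effect are untouched.

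**Working it through.** The plan gives no figure on this point to reproduce. The check compares the texts and then counts exposures.

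**1. Does the regimen create the exposure?** Site (back of the neck) and time (morning) appear in the Directions and again in Procedures. Bergamot peel oil is on the ingredient list. Because carrier oils are already in the blend, the dilution sentence means that no *further* dilution is normally needed; it does not mean that neat essential oil is applied.

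**2. Does the protocol regard it as a hazard?** Yes: in the Adverse Events section, in the bergamot row of Table 2 and in Primary Hypothesis 3.

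**3. Is there a preventive instruction anywhere in the available text?**

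| Place | What it provides | Prevents or reacts |
|---|---|---|
| Procedures | Physician discusses side effects (content unspecified) and can adjust dose or route | Possibly prevents; reacts |
| Table 1 | AE review and skin exam, V3 to V10 | Reacts |
| Adverse Events | Unscheduled visit at the investigator's discretion | Reacts |
| Human Subjects, Risks | Names skin irritation and breast enlargement, refers to Table 2 | Pointer only; sun not named |
| Human Subjects, Minimization of risk | Physician skin check at each visit, with power to stop or switch route; phone numbers | Reacts |

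No place tells families to cover treated skin or keep it out of the sun.

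**4. Exposure counts.** Inputs are 12 weeks per condition (Data Analytic Plan; Table 1 note), the visit weeks in Table 1, and one topical session each morning. Daily use is inferred from the instruction to apply in the morning.

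- Standard regimen: 12 weeks × 7 days = 84 morning topical applications.
- Switched to diffusion only: 0 topical sessions.
- Switched to topical only: 2 × 84 = 168 sessions, of which 84 are in the morning.
- First scheduled skin exam, Reconnect first: Week 0 to V3 at Week 2 = 2 × 7 = 14 mornings.
- First scheduled skin exam, Reconnect second: V7 at Week 16 to V8 at Week 20 = (20 − 16) × 7 = 28 mornings.
- Earliest report: a phone call on the first day, after 1 application.

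A reaction could thus come to attention after 1 to 14 mornings (Reconnect first) or 1 to 28 mornings (Reconnect second).

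**The case against.** The strongest reply is that the printed directions may not be what families see. The trial is double-blind, and these directions name the active product, so handing them out unchanged would break the mask. A masked sheet is likely, and it is not among the documents. The consent form, a usual place for a sun warning, was also removed. In addition, the physician is to discuss side effects, and sun sensitivity comes first in the protocol's own list of potential AEs, so the discussion would naturally cover it. Finally, no harm is shown: bergamot is one of 17 listed ingredients, the neck dose is a single drop, and no reaction rate is given.

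Much of this stands as a limit. It cannot be said that families received no sun advice, and the size of the risk cannot be judged. It does not remove the point about the printed regimen. The plan specifies a site and a time that produce the exposure. The side-effect discussion is not tied to sun advice, the Risks and Minimization of risk text does not mention sun, and the skin checks act once a reaction has occurred. If a warning does exist elsewhere, bringing the directions into line with it costs almost nothing.

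The same Table 2 row also advises against bergamot in children younger than 5, while eligibility begins at 3. That is a separate matter, and the present point does not depend on it.

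**Conclusion.** The concern holds for the directions as printed in the protocol: a bergamot-containing blend goes on the back of the neck in the morning with no sun precaution, although the protocol names the hazard. In size, it amounts to 84 morning applications per child on the standard regimen, with up to 14 or 28 of them before the first scheduled skin exam, depending on order. This assumes daily use; that the neck is exposed to light is a further assumption. Because the bergamot fraction and reaction rate are unknown, these counts cannot be turned into an expected number of reactions. It is a minor safety improvement for the sponsor to consider, held with medium confidence because the consent form and any masked instruction sheet could not be seen.

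**What to change.** Add one line to the topical directions, identical for both coded oils and consistent with any consent wording: *After application, keep the treated skin covered or out of direct sun.* If families receive a separate masked sheet, put the same line there.

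Optionally, add a yes/no photosensitivity prompt to the existing skin exam at V3 to V10, so that the event named in Hypothesis 3 is actively asked about in both conditions. Recording AEs and tabulating them by type are already planned, so only the asking would be new.

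The cost is one sentence and, if wanted, one item on an existing exam. There are no added visits or procedures, and identical wording protects the blind. The trade-off is that the photosensitivity rate would then be observed with the precaution in place, in both conditions, and should be reported as such.
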